7.3.4 FINAL STUDY VISIT

Visit 3, Week 12 (\pm 7 days)

Subjects may return to the clinic twelve weeks after the treatment. Adverse events, weight and any changes to concomitant medications will be recorded.

Subjects will be asked to complete the lifestyle, 5-point Likert subject satisfaction and treatment evaluation questionnaires. Measurement of the abdominal circumference will be made with the sponsor supplied tape measure using the marked boundaries as a guide for replication.

Photographs of the marked treatment area followed by ultrasound measurements of the marked treatment area will be made as per the instructions supplied by the sponsor.

The End of Study form will be completed and subjects will be discharged from the clinic and terminated from the study.

The PI will record all reportable events with start dates occurring any time after informed consent is obtained until 7 (for non-serious AEs) or 30 days (for SAEs) after the last day of study participation.

7.3.5 EARLY TERMINATION VISIT

Subjects who terminate the study early for whatever reason, will be asked to provide a reason for their early termination. Adverse events and the reason for early termination will be recorded.

7.3.6 UNSCHEDULED VISIT

If an unscheduled visit occurs, the reason for the unscheduled visit will be documented. If the unscheduled visit is the result of an adverse event, the event will be recorded on the adverse event CRF.

7.3.6 SCHEDULE OF EVENTS TABLE

Procedures	Screening (-6 weeks)	Enrollment/Treatment (Visit 1, Day 0)	Follow-up 1 Visit 2, Week 6 (± 3 days)	Follow-up 2 Visit 3, Week 12 (± 7 days)
Informed consent	X			
Inclusion/exclusion criteria	X	X		
Demographics	X			
Medical history	X			
Physical exam	X			
Weight		X	X	X
Urine pregnancy test ^a	X			
Lifestyle Indicator Questionnaire		X		X
Abdominal circumference		X	X	X
Photographs		X	X	X
Ultrasound subcutaneous fat		X	X	X
Administer Treatment		X		
Discomfort/Pain Visual Pain Scale		X		
PI immediate response		X		
Blinded reviewers GAIS		X		X
Subject satisfaction questionnaire				X
Treatment evaluation questionnaire				
Concomitant medication	X	X	X	X
Adverse event evaluation		X	X	X

7.4 JUSTIFICATION FOR SENSITIVE PROCEDURES

N/A

7.5 CONCOMITANT MEDICATIONS, TREATMENTS, AND PROCEDURES

All concomitant prescription medications taken during study participation will be recorded on the case report forms (CRFs). For this protocol, a prescription medication is defined as a medication that can be prescribed only by a properly authorized/licensed clinician. Other medications to be reported in the CRF are concomitant over-the-counter medications and non-prescription medications.

7.6 PROHIBITED MEDICATIONS, TREATMENTS, AND PROCEDURES

The use of immunosuppressive medications, antiplatelet medications, thrombolytics, anti-inflammatory medications and anticoagulant medications is to be avoided. Herbal supplements, perfumes, cosmetics and/or medications that may affect sensitivity to light are prohibited. The use of Accutane™ (Isotretinoin) within the past six months is also strictly prohibited.

7.7 PROPHYLACTIC MEDICATIONS, TREATMENTS, AND PROCEDURES

None.

7.8 RESCUE MEDICATIONS, TREATMENTS, AND PROCEDURES

In the event that the subject experiences pain, the principal investigator may prescribe any analgesic deemed appropriate to the level of pain. If a subject experiences any first, second or third degree burn or pain beyond narcotics, then the following procedure will be implemented:

Immediate triage and treatment of the patient shall be determined by the treating physician and based upon severity and type of burn identified.

The event will be reported to the study Director within 24 hours of occurrence. If the event meets the criteria of a SAE, then it must be reported on the SAE form.

A copy of the patient chart and treatment parameters are to be forwarded to the study Director within 24 hours.

The study Director will be responsible for issuing a written report to the company and the IRB Chairman no later than 7 days from the incident.

Long term follow up and care shall continue at the discretion of the treating physician.

All patients experiencing a complication of the device will be followed a minimum of 2 years following the initial injury. Longer care and observation will be at the discretion of the treating physician.

All minor complications such as appearance or altered sensation, except for pain, can be reported within 30 days of patient complaint. Both chart and treatment parameters are to be provided to the study Director and shared with the company and IRB chairman.

8 ASSESSMENT OF SAFETY

8.1 SPECIFICATION OF SAFETY PARAMETERS

In addition to spontaneous reports of adverse events, subjects will complete a 10 cm discomfort/pain visual pain scale and the principal investigator will examine the treated area and report immediate response.

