2.3 POTENTIAL RISKS AND BENEFITS

2.3.1 KNOWN POTENTIAL RISKS

Expected adverse events of the laser treatment procedure include transient tenderness, erythema, edema, and/or induration in the treated area lasting from one to three weeks after the treatment. In addition, other adverse events may include and include localized firmness, ecchymosis, skin burn, hyperpigmentation, hypopigmentation, blister and changes in skin laxity. Rarely, skin contour irregularities, dimpling, asymmetry (uneven appearance due to uneven anatomy or uneven treatment of the area), necrosis (tissue death), hardness and nodules occur. Protective laser eyewear will be worn by the subject and operator providing the procedure.

The device has a contact tissue cooling system in place during the procedure to minimize thermal discomfort and prevent damage to the treatment area. Expected adverse events related to the contact cooling include tingling, itching, decreased sensation, numbness, erythema and tenderness.

The boundaries of the treatment area will be marked with a semi-permanent tattoo ink using a microblade. The ink markings should dissipate within one year. Microblade marking may be associated with tenderness.

There are minimal risks associated with the use of ultrasound. The use of the ultrasound may cause redness of the skin. Skin rashes rarely occur with the use of ultrasound gel.

Risks will be mitigated by conducting this protocol with an investigator experienced in the therapeutic area of the clinical investigation. The investigator will be trained by the sponsor on the use of the device. The device design incorporates safety mechanisms which minimize risks. Patients will also be rigorously screened prior to their enrollment and rigorously followed over the course of the study.

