7.3.2 ENROLLMENT/BASELINE

Enrollment/Baseline/Treatment Visit (Visit 1 – Day 0)

Pre-Treatment

The investigator will confirm that the subject continues to meet the inclusion and none of the exclusion criteria. Adverse events, weight and any changes to concomitant medications will be recorded. The subject will complete the modified Simple Lifestyle Indicator Questionnaire (SLIQ).

The location and size of the treatment area will be left to the principal investigator's judgement based on his/her assessment of individual subject requirements for treatment. The defined abdominal treatment area will be marked with a semi-permanent pigment using a treatment template as per the sponsor's instructions. Photographs of the marked treatment area followed by ultrasound measurements of the marked treatment area will be made as per the instructions supplied by the sponsor. Measurement of the abdominal circumference will be made with the sponsor supplied tape measure using the marked boundaries as a guide for replication.

Treatment

Protective eye goggles will be worn by both the patient and site staff performing the treatment for the duration of the treatment session.

Based on the mild nature of treatment, anesthesia is not required. The treatment procedure should include positioning of the patient in a manner that enables access to the target treatment anatomical site.

The belt will be positioned on the subject as per the marked treatment template. Laser applicators will be secured in place by the belt with the areas treated for up to 25 minutes. The laser energy will be delivered to the area while cooling is administered to the skin surface to increase subject comfort. Treatment will continue until the total treatment area has been treated. The subject will receive one treatment session only.

The assessment of discomfort/pain during the treatment procedure will be assessed using the Wong-Baker Faces Pain rating scale with treatment parameters adjusted according to patient's comfort level.

Post Treatment

Assessment

The investigator will examine the treated areas and report immediate response (pain during treatment, hemorrhage, burn, erythema, edema, purpura) using a 5 point scale: 1=none; 2=trace; 3=moderate; 4=marked; 5=severe.

The assessment of discomfort/pain based on the subject's completion of the 10 cm visual pain scale should also be documented immediately after treatment.

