8.3 TIME PERIOD AND FREQUENCY FOR EVENT ASSESSMENT AND FOLLOW-UP

The occurrence of an AE or SAE may come to the attention of study personnel during study visits and interviews of a study participant presenting for medical care, or upon review by a study monitor. All AEs

including local and systemic reactions not meeting the criteria for SAEs will be captured on the appropriate CRF. Information to be collected includes event description, time of onset, clinician's assessment of severity, relationship to study product (assessed only by those with the training and authority to make a diagnosis), and time of resolution/stabilization of the event. All AEs occurring while on study must be documented appropriately regardless of relationship. All AEs will be followed to adequate resolution.

Any medical condition that is present at the time that the participant is screened will be considered as baseline and not reported as an AE. However, if the study participant's condition deteriorates at any time during the study, it will be recorded as an AE. UPs will be recorded in the data collection system throughout the study.

Changes in the severity of an AE will be documented to allow an assessment of the duration of the event at each level of severity to be performed. AEs characterized as intermittent require documentation of onset and duration of each episode.

The PI will record all reportable events with start dates occurring any time after informed consent is obtained until 7 (for non-serious AEs) or 30 days (for SAEs) after the last day of study participation. At each study visit, the investigator will inquire about the occurrence of AE/SAEs since the last visit. Events will be followed for outcome information until resolution or stabilization.

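### No structured examination of the treated area for the local effects listed in 2.3.1 is prescribed at Week 6 or Week 12, so mild or symptomless effects may be under-counted

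*Combined protocol and SAP*

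**What the plan says.** **Listed effects.** Section 2.3.1 names, among possible adverse events, "hyperpigmentation, hypopigmentation, blister and changes in skin laxity". It continues "Rarely, skin contour irregularities, dimpling, asymmetry", and the same sentence goes on to necrosis, hardness and nodules.

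**Examination after treatment.** Section 8.1 states that, in addition to spontaneous AE reports, "subjects will complete a 10 cm discomfort/pain visual pain scale and the principal investigator will examine the treated area and report immediate response". Section 7.3.2 gives the content: "The investigator will examine the treated areas and report immediate response (pain during treatment, hemorrhage, burn, erythema, edema, purpura) using a 5 point scale". In the schedule of events, the row "PI immediate response" is marked at Visit 1 only, and the physical examination is marked at screening only.

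**Follow-up visits.** For Week 12, section 7.3.4 says "Adverse events, weight and any changes to concomitant medications will be recorded". Section 7.3.3 says the same for Week 6. Both sections then list circumference, photographs and ultrasound. The schedule marks an AE evaluation at both visits, and section 8.3 gives the method: "At each study visit, the investigator will inquire about the occurrence of AE/SAEs since the last visit".

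**Safety analysis.** Section 10.4.5 draws on spontaneous AE reports, the pain scale, a response questionnaire and the Day 0 immediate response. Its AE summaries count subjects with any AE, any serious AE, or withdrawal due to an AE. It plans no count by type of local effect at Week 6 or Week 12.

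**The concern.** Safety is half of the stated objective, and treatment-related AEs are a safety endpoint. For an aesthetic device, the effects most relevant to a prospective user include visible or palpable changes in the treated area. Several of those named in 2.3.1 can be mild and painless, so a subject who is asked a general question about adverse events may not mention them.

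There is no concurrent control arm to reveal an under-count, and with up to five sites the habit of looking may differ from site to site. A low reported rate could then partly reflect the method of ascertainment.

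Detection also has consequences within the protocol. Section 7.8 ties extended follow-up to a subject having a device complication, and it times the reporting of minor appearance complications from the patient's complaint. Section 7.3.4 discharges subjects at Week 12.

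**Working it through.** The plan states no figure on this point, so there is none to reproduce. The check is a comparison of sections, followed by an illustration.

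**Step 1. Effects against examinations**

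| Effect listed in 2.3.1 | Among the Day 0 items (7.3.2)? | Inspection prescribed at Week 6 or 12 (7.3.3, 7.3.4, schedule)? |
|---|---|---|
| Hyper- or hypopigmentation | No | No |
| Change in skin laxity | No | No |
| Contour irregularity, dimpling, asymmetry | No | No |
| Hardness, nodules | No | No |

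The Day 0 items are pain, hemorrhage, burn, erythema, edema and purpura. None of the effects in the table is among them.

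**Step 2. Could Day 0 have served?** Section 2.3.1 gives no onset times, so calling these effects late is an inference. It is a reasonable one for changes that follow fat loss: section 2.1 places results at 6 weeks and the best result at 12, so a contour change caused by that loss would not be visible just after treatment.

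**Step 3. Use of the follow-up images.** Photographs serve the primary endpoint (4.2.1, 10.4.2), and ultrasound serves the adipose-thickness endpoint (4.2.2, 10.4.3). No section assigns either of them a safety reading.

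**Step 4. What incomplete capture would do (illustration only)**

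Inputs: n = 50, the maximum enrolment (10.5). Let s be the share of true events that are recorded. The values of s below are assumed, because the documents give none. Section 2.3.1 calls contour irregularity, dimpling, asymmetry, necrosis, hardness and nodules rare but gives no rate, so the true rates p = 1% and 2% are also assumed.

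*Zero events recorded.* The one-sided 95% upper bound on the recorded rate is 1 − 0.05^(1/50) = 5.8%. Dividing by s gives the bound on the true rate:

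- s = 1: 5.8%
- s = 0.75: 5.8% / 0.75 = 7.8%
- s = 0.50: 5.8% / 0.50 = 11.6%
- s = 0.25: 5.8% / 0.25 = 23.3% (from the unrounded 5.816%)

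*Chance of recording at least one event*, 1 − (1 − p·s)^50:

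| True rate p | s = 1 | s = 0.50 | s = 0.25 |
|---|---|---|---|
| 2% | 1 − 0.98^50 = 64% | 1 − 0.99^50 = 39% | 1 − 0.995^50 = 22% |
| 1% | 1 − 0.99^50 = 39% | 1 − 0.995^50 = 22% | 1 − 0.9975^50 = 12% |

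In expected counts the loss is small. At p = 2% there is 50 × 0.02 = 1 true case, of which 0.5 (s = 0.50) or 0.25 (s = 0.25) would be recorded. The practical effect falls on what a zero in the table can be taken to mean.

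**The case against.** The strongest reply is that the protocol does have surveillance at follow-up. An AE evaluation is scheduled at Weeks 6 and 12, and the investigator asks about events at every visit (8.3). Staff photograph, scan and tape-measure the area at both visits, and section 8.3 accepts that events may come to notice during visits. Section 8.2.2 says that a doubtful clinical observation should be reported, 8.4.1 allows individual signs to be reported as AEs, and 7.3.2 requires other or persisting side effects to be recorded. A response questionnaire feeds the safety analysis (10.4.5) and a treatment evaluation questionnaire is completed at Week 12 (7.3.4). Their contents are not in the documents, and neither is the AE form, so any of them might prompt for local effects.

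All of this stands, and it rules out three stronger readings that a reader might infer:

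- *No visit looks for these effects, or the skin is seen only on Day 0.* Not supported. Both follow-ups carry an AE evaluation, the area is handled and imaged, and it is also examined for eligibility at screening (7.3.1).
- *Capture depends on subjects volunteering complaints.* Not supported. The inquiry is active, and staff observation is a permitted route.
- *A common effect would be reported at a fraction of its true rate.* One could assume a 10% rate with 30% to 70% captured and obtain 3% to 7%. Neither input is in the documents, and 10% sits badly with 2.3.1, which calls most of these effects rare.

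The reply does not remove the gap. Permission to report what is noticed is not an instruction to look. Without a prescribed inspection there is no record that a subject was checked and found clear, and so no sound denominator for each effect.

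**Conclusion.** The point holds as a limitation of ascertainment. The documents do not contradict themselves here, and surveillance is not absent. After treatment, the only prescribed examination of the treated area is on Day 0 and covers six acute items. For the effects in the table, follow-up capture rests on inquiry, spontaneous report and incidental observation, and the images taken at both visits have no stated safety reading. Mild or symptomless effects may be under-counted.

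The size cannot be derived from the documents. The bounds of 5.8% to 23.3% for zero recorded events assume 50 evaluable subjects and capture between 100% and 25%; they show sensitivity and do not estimate this trial's loss. The conclusion also assumes that the unseen questionnaires and AE form do not already contain a structured local-effects check. If they do, the protocol should say so, and the concern would shrink accordingly. The change is worth making because it is cheap and bears on a stated endpoint.

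**What to change.** 1. **Sections 7.3.2 to 7.3.4, section 8.1 and the schedule table:** add a brief investigator inspection of the treated area before treatment on Day 0 and at Visits 2 and 3. Use a yes/no and severity checklist of the local effects already listed in 2.3.1.
2. **AE rule:** record as an AE only a finding that is new or worse than on the pre-treatment checklist. Section 8.3 treats conditions present at screening as baseline. Some asymmetry, mild laxity or pigment variation may pre-exist, since 5.2 excludes only severe laxity. Without the baseline checklist, such features would be counted as AEs.
3. **Marking:** have the checklist separate the semi-permanent boundary pigment from true pigment change. Section 2.3.1 expects the marking to take up to a year to fade, so it may still be visible at Weeks 6 and 12.
4. **Section 10.4.5:** add the number (%) of subjects with each new or worsened effect at Week 6 and at Week 12, with the number inspected as the denominator.

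The cost is one CRF page and a few minutes at visits where the area is already exposed for photographs and ultrasound. No visit is added. The downside is that more minor AEs will be reported.

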8.1.1 DEFINITION OF ADVERSE EVENTS (AE)

Adverse event means any untoward medical occurrence associated with the use of an intervention in humans, whether or not considered intervention-related (21 CFR 312.32 (a)).

8.1.2 DEFINITION OF SERIOUS ADVERSE EVENTS (SAE)

NOTE: The term serious is not synonymous with severity, which may be used to describe the intensity of an event experienced by the subject). An AE that does not meet any of the below criteria will be classified as non-serious.

A serious AE is any event that:

- Results in, or contributes to a death;
- Is immediately life threatening (injury or illness);
- Results in hospitalization, or prolongs an existing hospitalization;
- Results in permanent impairment of body structure or function, or in persistent or significant disability/incapacity;
- Results in an injury that requires medical intervention to prevent permanent impairment of body structure or function;
- Is a device malfunction or deterioration in the characteristics and/or performance of the device that results in death or serious deterioration in health;
- Is a device malfunction or deterioration in the characteristics and/or performance of the device that, if it were to occur again, could result in death or serious deterioration in health;
- Results in a congenital anomaly or birth defect.
- Is any medically significant injury, event or experience that requires medical/surgical intervention to prevent one of the outcomes listed above;
- Results in end organ toxicity, including hematological, renal, cardiovascular, hepatic, gastrointestinal, and central nervous system events;

8.1.3 DEFINITION OF UNANTICIPATED PROBLEMS (UP)

This definition includes an unanticipated adverse device effect, any serious adverse effect on health or safety or any life-threatening problem or death caused by, or associated with, a device, if that effect, problem, or death was not previously identified in nature, severity, or degree of incidence in the investigational plan or application (including a supplementary plan or application), or any other unanticipated serious problem associated with a device that relates to the rights, safety, or welfare of subjects (21 CFR 812.3(s)).

8.2 CLASSIFICATION OF AN ADVERSE EVENT

8.2.1 SEVERITY OF EVENT

For AEs not included in the protocol defined grading system, the following guidelines will be used to describe severity.

- **Mild** – Events require minimal or no treatment and do not interfere with the participant's daily activities.
- **Moderate** – Events result in a low level of inconvenience or concern with the therapeutic measures. Moderate events may cause some interference with functioning.
- **Severe** – Events interrupt a participant's usual daily activity and may require systemic drug therapy or other treatment. Severe events are usually potentially life-threatening or incapacitating.

8.2.2 RELATIONSHIP TO STUDY AGENT

The clinician's assessment of an AE's relationship to the study agent is part of the documentation process, but it is not a factor in determining what is or is not reported in the study. If there is any doubt as to whether a clinical observation is an AE, the event should be reported. All AEs must have their relationship to study agent assessed. In a clinical trial, the study product must always be suspect. To help assess, the following guidelines are used.

- **Related** – The AE is known to occur with the study agent, there is a reasonable possibility that the study agent caused the AE, or there is a temporal relationship between the study agent and event. Reasonable possibility means that there is evidence to suggest a causal relationship between the study agent and the AE.
- **Not Related** – There is not a reasonable possibility that the administration of the study agent caused the event, there is no temporal relationship between the study agent and event onset, or an alternate etiology has been established.

